1.7 OVERALL DESIGN

This trial will be a multi-site open-label Phase II non-randomized pilot study involving two US sites: NIH Clinical Center and CNH. [name] and [name] at CNH will be involved in identifying and recruiting potential participants. They will be involved in answering questions about the study from interested patients but will not be screening or obtaining consent from participants. They will also be analyzing identifiable information from participants. All study visits will be conducted at a single site (NIH Clinical Center) to investigate the efficacy of liraglutide, a glucagon-like peptide-1 (GLP1) analogue to promote weight loss in pediatric patients (age 12 to <21y) who continue to have obesity (BMI ≥ 30 kg/m² or BMI $\geq 95^{\text{th}}$ percentile for age and sex) 1 year or more after vertical sleeve gastrectomy (SG) over 16 weeks.

Participants will undergo a telephone screening, followed by a screening visit to assess eligibility. Those found eligible will undergo a baseline evaluation to assess their glucose tolerance, lipids, levels of plasma GI hormones, appetite, body composition, energy intake, free living physical activity (by accelerometry), questionnaire measures, including assessment of weight related quality of life, mood, suicidality, and self-perception of body image. The trial will be divided into two consecutive periods. Period 1 will consist of 5 weeks of dose titration with goal of reaching max dose of 3 mg liraglutide daily with visits every 4 weeks over 16 weeks (including the 5 weeks of titration). The treatment period will then be followed by a 12-week period off study drug ending at week 28.

The primary outcome (change in BMI) will be statistically analyzed after participants have been treated with 3.0 mg daily liraglutide or max tolerated dose at 16 weeks. Secondary outcomes will also be measured at 16 weeks. BMI will be reassessed at follow-up at 28 weeks. There will be no interim analyses. Randomization will be stratified by birth sex assignment (Male versus Female), race (Non-Hispanic Black versus Other), and degree of weight loss after SG (those with typical post-SG weight loss, defined as $\geq 20\%$ BMI reduction versus those with poor post-surgical weight loss response, defined as $< 20\%$ BMI reduction post-SG), since expectation of benefit might differ in those unable to lose weight with SG.

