1.30 STATISTICAL HYPOTHESIS

- Primary Endpoint:

The Primary Endpoint is estimation of required sample size for a later RCT through calculation of effect size for change in body mass index (BMI) from baseline to 16 weeks of liraglutide. The hypothesis is: The data will be sufficient to calculate the effect size for change in BMI from baseline to 16 weeks for a 2-group experiment (placebo versus liraglutide).

- Secondary Endpoint(s):

There are 3 sets of key secondary endpoints:

- A. Changes in BMI and fat mass after 16 weeks of liraglutide.
- B. Comparison of changes in BMI and fat mass after 16 weeks liraglutide in participants who had a poor initial response to SG (<20% BMI reduction at BMI nadir) vs. those with a typical post-SG weight loss ($\geq 20\%$ BMI reduction at BMI nadir)
- C. Tolerability and safety of 3.0 mg Liraglutide

Statistical hypothesis A: there will be a statistically significant decrease in BMI and fat mass after 16 weeks of liraglutide.

Statistical hypothesis B: there will be a statistically significant greater decrease in BMI and fat mass after 16 weeks of liraglutide in participants in who had a typical post-SG weight loss vs. those who had a poor initial response to SG.

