1.31 SAMPLE SIZE DETERMINATION

As this is a pilot investigation to determine the sample size of a fully powered investigation, no formal sample size determination is necessary. That said, the study is powered such that it might be able to detect a moderate-to-large difference from treatment. A recent randomized, double-blind, placebo-controlled phase 3 trial of liraglutide for adolescents (age 12 to <18 years) with obesity ($BMI \geq 30 \text{ kg/m}^2$ and $\geq 95^{\text{th}}$ percentile for age and sex) [32] reported a -1.39 kg/m^2 ($SE=0.31$, $n=125$) difference over 1 year of liraglutide treatment. If that effect size is replicated and if a similar SD (3.46) is found in the present study, we estimate that a total sample size of 40 subjects will have 80% power (β) to detect a -1.39 kg/m^2 difference in BMI (effect size = -

Abbreviated Title: Liraglutide in Teens Post-SG

Version Date: 1/30/23

0.4017) at level of significance of 0.05 (1-sided, as we are interested only in BMI loss). See **Table 2**.

t-test - Means: Difference between two dependent means (matched pairs) Tails = 1, $\alpha = 0.05$, Effect size dz = 0.4

[figure not shown]

Table 2, drawn using data obtained using G-Power 3.1.9.2 [90, 91]

We anticipate that virtually all participants who sign consent and are screened will qualify and agree to enroll. We will therefore attempt to recruit and screen in person no more than 50 adolescents, among whom no more than 43 will be treated with liraglutide in hopes of having 40 who complete the study. Based on prior studies in adolescents using liraglutide, we anticipate few dropouts or withdrawals by week 16. In Kelly et al's study of adolescents [32], 119/125 (95%) of those treated with liraglutide remained on-treatment at week 16.

As a pilot investigation, there is no assumption that there will be adequate power for any of the secondary outcomes investigated. We will, however, be able to use the data to determine power in a future randomized controlled trial for these outcomes.

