1.33 STATISTICAL ANALYSES

1.33.1 General Approach

Tabulations will be produced for appropriate demographic, baseline, efficacy, and safety parameters. For categorical variables, summary tabulations of the number and percentage of subjects within each category of the parameter will be presented. For continuous variables, the number of subjects (N), mean, median, standard deviation (SD), minimum, and maximum values will be presented.

Formal statistical hypothesis testing will be performed on endpoints with testing conducted at the 1-sided, 5% level of significance. Summary statistics will be presented, as well as confidence intervals (Cis), as described in the sections below. Trial success will be based on a p-value <0.05.

Covariates to be modeled are pre-specified in the sections below. Results of statistical procedures for efficacy outcomes involving covariates will be presented as adjusted means (least-squares means) with standard errors.

Checks of assumptions (e.g., normality) underlying statistical procedures will be performed and corrective procedures will be applied. It is expected that log transformation will be used for the primary outcome and most secondary outcomes. Percentage data will be arcsin (square root (value)) transformed for analysis.

Unless otherwise noted, all statistical analyses will be performed using SPSS statistical software Version 25 (IBM Corp, Armonk, NY) or higher.

Subject disposition will be tabulated and include the number screened, the number randomized, the number treated in total, the number dosed with liraglutide, the number in each subject population for analysis, and the number who withdrew prior to completing the study and reason(s) for withdrawal.

A by-subject data listing of study completion information including the reason for premature study withdrawal, if applicable, will be made available. Subject disposition will include patients in the Screening Analysis Dataset.

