1.33.2 Analysis of the Primary Endpoint

The Primary Endpoint is estimation of required sample size for a later RCT through calculation of effect size for change in body mass index (BMI) from baseline to 16 weeks of liraglutide. The statistical hypothesis is: The data will be sufficient to calculate the effect size for change in BMI from baseline to 16 weeks for a 2-group experiment (placebo versus liraglutide). The primary outcome could be stated as the percentage of participants who are in the Per Protocol Dataset (who complied with the protocol sufficiently to ensure that these data would be likely to represent the effects of treatment according to the underlying scientific model (i.e., participants who took at least 80% of study intervention for 80% of the days within the treatment period). The study will be considered successful if more than 80% complete the trial.

The key variable that will be calculated is the effect size of the investigation. This value will be determined using the observed mean change in BMI from baseline to 16 weeks and the standard deviation for mean change observed with liraglutide treatment. The effect size (in this case, the Standardized Mean Difference (SMD) between two groups) will be calculated using Gpower 3.1.9.2 [90, 91] assuming the same standard deviation for both liraglutide-treated and control groups, a similar sample size for each group, and the observed difference in BMI from baseline to 16 weeks as the outcome of interest. Cohen's $d = (M_1 - M_2)/SD_{pooled}$. A plot will be created showing a range of sample sizes required for a between-groups t-test. For example, if we use the data from a recent randomized, double-blind, placebo-controlled phase 3 trial of liraglutide for adolescents who had not previously undergone bariatric surgery but had obesity [32], the liraglutide reduced BMI by -1.39 kg/m^2 ($SE=0.31$, $n=125$ over 1 year of treatment and the placebo group increased BMI by 0.19 kg/m^2 ($SE=0.33$, $n=126$) over the sample interval. If we found a similar reduction in BMI in adolescents who have obesity after bariatric surgery, the estimated effect size $d=0.4566$ (a difference of 1.58 kg/m^2 between groups with $SD 3.46$), a total sample size of 120 (60 per group) would be needed for one-sided $\alpha=0.05$ and power of 0.80 (Table 1).

[figure not shown]

Table 1, drawn using data obtained using G-Power 3.1.9.2 [90, 91]

Abbreviated Title: Liraglutide in Teens Post-SG

Version Date: 1/30/23

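### Two study-level success rules, p<0.05 in 1.33.1 and more than 80% completing in 1.33.2, are neither ranked nor combined, so one dataset can pass one rule and fail the other

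*Combined protocol and SAP*

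**What the plan says.** Two sentences in current text each define success for the whole study.

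- Section 1.33.1 (General Approach), after setting a one-sided 5% level for hypothesis tests: "Trial success will be based on a p-value <0.05". It names no endpoint, test or dataset.
- Section 1.33.2 (Analysis of the Primary Endpoint): "The study will be considered successful if more than 80% complete the trial". Just before this, the same section offers another wording: "The primary outcome could be stated as the percentage of participants who are in the Per Protocol Dataset".

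Other sections bear on which test the p-value rule could mean.

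- Section 1.30 makes the primary endpoint an estimation task with the hypothesis "The data will be sufficient to calculate the effect size for change in BMI from baseline to 16 weeks". The test of change is secondary: "Statistical hypothesis A: there will be a statistically significant decrease in BMI and fat mass after 16 weeks of liraglutide".
- Section 1.7 says "The primary outcome (change in BMI) will be statistically analyzed".
- Section 1.31 gives a power calculation for "Difference between two dependent means (matched pairs) Tails = 1", based on BMI change.
- Section 1.33.1 also says "It is expected that log transformation will be used for the primary outcome and most secondary outcomes", which fits a measured variable better than a sample-size estimate.

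**The concern.** The primary endpoint in 1.30 and 1.33.2 has no null-hypothesis test, so it yields no p-value for the rule in 1.33.1 to act on. The rule must refer to something else. Change in BMI is the likely candidate, given 1.7 and 1.31, but 1.30 and 1.33.3 class that test as secondary and the plan does not make the link.

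The completion rule uses a different quantity. A study can keep nearly everyone and show no significant fall in BMI, or show a clear fall and lose too many participants. The plan does not say what is reported in either case, so the label could be settled after both results are known.

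The threshold in 1.33.2 has a smaller looseness of its own. It follows a sentence on Per Protocol membership but is applied to completing the trial. Under 1.22, a participant who stops the drug remains in the study, so the two counts need not agree.

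**Working it through.** **Inputs from the documents.** One-sided alpha 0.05 (1.31, 1.33.1). Planning mean change -1.39 kg/m² with SE 0.31 and n=125 over 1 year, SD 3.46 (1.31, 1.33.2). At most 43 treated, 40 hoped to complete (1.31). 119 of 125 still on treatment at week 16 in the cited adolescent trial (1.31).

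**Inputs assumed.** Baseline BMI 37 for the log-scale check; section 1.4 cites 37 three years after sleeve gastrectomy. The 16-week SD is not given, so 3.46 is carried over. Retention of 95.2% is taken as the completion rate. Completion is treated as independent of BMI change. All 43 treated are analysed. Completion rates of 90%, 85% and 80% are shown as a range.

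**Step 1: the plan's power figure.** SD = 0.31 × √125 = 3.47, against 3.46 stated. Effect size = 1.39 / 3.46 = 0.4017. Noncentral-t power for a one-sided paired test at n=40 is 0.803, so the stated 80% reproduces. At n=43 it is 0.828.

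**Step 2: the completion threshold.** 0.8 × 43 = 34.4, so more than 80% means at least 35 of 43 (81.4%). For 40 treated it means at least 33 (82.5%), because 32/40 is exactly 80%.

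**Step 3: a dataset that splits the rules.** 41 of 43 complete (95.3%), so 1.33.2 is met. Mean change -0.60, SD 3.46.
- Untransformed: t = -0.60 / (3.46 / √43) = -1.137 on 42 df, one-sided p = 0.131.
- Log scale, second-order approximation: mean log change = -0.60/37 - (3.46² + 0.60²)/(2 × 37²) = -0.0162 - 0.0045 = -0.0207. The SD is about 3.46/37 = 0.0935, so t is about -1.45 and p about 0.08. Simulated sets of 43 changes with exactly that mean and SD give a median p of 0.081.

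The p-value rule fails on either scale.

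**Step 4: the reverse split.** 34 of 43 complete (79.1%), so 1.33.2 is not met. Mean change -1.39 gives t = -2.634 and p = 0.006 (about 0.003 on the log scale; untransformed p = 0.013 if only the 34 completers are analysed). The p-value rule passes.

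**Step 5: how often the rules disagree.** With power P = 0.828 and C the binomial probability that at least 35 of 43 complete, disagreement = (1 - P) × C + P × (1 - C).

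| Completion rate | C | Completion met, test missed | Test met, completion missed | Total |
|---|---|---|---|---|
| 95.2% (cited) | 0.9998 | 17.2% | 0.01% | 17% |
| 90% (assumed) | 0.976 | 16.8% | 2.0% | 19% |
| 85% (assumed) | 0.813 | 14.0% | 15.5% | 29% |
| 80% (assumed) | 0.500 | 8.6% | 41.4% | 50% |

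**Step 6: dependence on scale.** At n=43 and SD 3.46, the smallest mean fall that reaches p<0.05 is 1.682 × 3.46 / √43 = 0.89 kg/m² untransformed, but about 0.74 on the log scale with baseline 37. A fall of 0.80 gives p = 0.068 untransformed and about 0.040 on the log scale. The SD above which the -0.60 example is non-significant is 0.60 × √43 / 1.682 = 2.34 untransformed and about 2.7 on the log scale. Any cut-off has to be read with its scale.

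**The case against.** The best defence is that the specific section governs the general one. On that reading, the sentence in 1.33.1 closes a paragraph on test levels and only sets the threshold for individual tests, while 1.33.2 decides whether the study succeeded. Section 1.33.3 supports this by separating the secondary tests from the primary endpoint. This may well be what was meant. But no section says so, the sentence in 1.33.1 speaks of the trial's success without qualification, and 1.7 and 1.31 treat BMI change as the outcome to be tested. The defence shows that the repair is easy, not that the text is already clear.

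A second argument is that little depends on the label. This is an uncontrolled pilot, no formal decision is tied to either rule, and both disposition and the paired tests will be reported. That stands, and it limits the severity.

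A third is that the 17% is essentially one minus power. That is right at the cited retention: it is an ordinary missed test. It still produces opposite verdicts. The reverse split is remote there, since 34 or fewer of 43 completing has probability about 0.0002.

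A reader might also infer that completion and Per Protocol status will give different answers. The documents allow this but do not show how likely it is. Section 1.38 moves from staying on drug through week 16 to a Per Protocol threshold, which suggests that the sponsor treats the two as nearly the same. This part is imprecise wording and secondary to the main point.

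**Conclusion.** The point holds as a conflict between two stated success rules. Both are current and unqualified, nothing ranks or combines them, and the same data can satisfy one and fail the other. Under the plan's planning effect, with 95.2% retention taken as completion and independence assumed, this happens about 17% of the time, almost always as completion met with a non-significant test. The total rises to 29% at 85% completion, where about 15% is the reverse split. The -0.60 example holds on both scales at SD 3.46, but with a 16-week SD below about 2.3 (untransformed) or 2.7 (log scale) it would be significant.

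Two stronger readings are not supported. One is that the conflict damages the planning figure for the later trial; the effect size is computed the same way under either rule. The other is that the rules cannot be reconciled; a sensible precedence exists and only needs to be written down. The harm is confined to a reported verdict that can be chosen after the data are seen. It should be fixed before outcome analysis.

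**What to change.** State one success rule before the data are analysed. The option closest to 1.30 and 1.33.2 is:

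1. Delete the success sentence in 1.33.1, or reword it as the significance threshold for individual hypothesis tests, including secondary hypothesis A for both BMI and fat mass.
2. Keep the more-than-80% rule in 1.33.2. Give it one numerator (completion of a named visit, or Per Protocol membership) and one denominator. If the denominator is treated participants, the rule means at least 35 of 43, or 33 of 40.
3. Bring the primary-outcome wording in 1.7 and in the log-transformation sentence of 1.33.1 into line with 1.30.

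If the sponsor wants both rules, the plan should say that both must be met and name the test, scale and dataset. Any minimum BMI fall quoted should be given for both scales or left out.

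The cost is a short text amendment with no new data. The downside is one fewer route to declaring success: under the option above, a clear BMI fall with 34 of 43 completing would not count. If Per Protocol membership is the numerator, 1.32 must also say what the 80% of study intervention is measured against.

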1.33.2 Analysis of the Primary Endpoint

The Primary Endpoint is estimation of required sample size for a later RCT through calculation of effect size for change in body mass index (BMI) from baseline to 16 weeks of liraglutide. The statistical hypothesis is: The data will be sufficient to calculate the effect size for change in BMI from baseline to 16 weeks for a 2-group experiment (placebo versus liraglutide). The primary outcome could be stated as the percentage of participants who are in the Per Protocol Dataset (who complied with the protocol sufficiently to ensure that these data would be likely to represent the effects of treatment according to the underlying scientific model (i.e., participants who took at least 80% of study intervention for 80% of the days within the treatment period). The study will be considered successful if more than 80% complete the trial.

The key variable that will be calculated is the effect size of the investigation. This value will be determined using the observed mean change in BMI from baseline to 16 weeks and the standard deviation for mean change observed with liraglutide treatment. The effect size (in this case, the Standardized Mean Difference (SMD) between two groups) will be calculated using Gpower 3.1.9.2 [90, 91] assuming the same standard deviation for both liraglutide-treated and control groups, a similar sample size for each group, and the observed difference in BMI from baseline to 16 weeks as the outcome of interest. Cohen's $d = (M_1 - M_2)/SD_{pooled}$. A plot will be created showing a range of sample sizes required for a between-groups t-test. For example, if we use the data from a recent randomized, double-blind, placebo-controlled phase 3 trial of liraglutide for adolescents who had not previously undergone bariatric surgery but had obesity [32], the liraglutide reduced BMI by -1.39 kg/m^2 ($SE=0.31$, $n=125$ over 1 year of treatment and the placebo group increased BMI by 0.19 kg/m^2 ($SE=0.33$, $n=126$) over the sample interval. If we found a similar reduction in BMI in adolescents who have obesity after bariatric surgery, the estimated effect size $d=0.4566$ (a difference of 1.58 kg/m^2 between groups with $SD 3.46$), a total sample size of 120 (60 per group) would be needed for one-sided $\alpha=0.05$ and power of 0.80 (Table 1).

[figure not shown]

Table 1, drawn using data obtained using G-Power 3.1.9.2 [90, 91]

Abbreviated Title: Liraglutide in Teens Post-SG

Version Date: 1/30/23

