1.33.9 Exploratory Analyses

Any of the exploratory evaluations that generate quantitative measures will be examined using descriptive statistics including confidence intervals when appropriate. Any statistical tests (paired t-tests of baseline versus 16-week results) performed for evaluation of exploratory objectives will be done without formal adjustment for multiple comparisons, but in the context of the number of tests performed.

The following dependent variables will be examined in the dataset:

Change in: BMI standard deviation score for age and sex, body weight, percentage total body fat mass by DXA, appetite score using visual analog scale, attention bias to highly palatable images, energy intake at buffet meal, free living physical activity by accelerometry, hemoglobin A1C, plasma GI hormones (GLP-1 and PYY), weight related quality of life score, Beck depression inventory total score, Columbia-Suicide Severity Rating Scale, body-esteem scale score for adolescents and adults, HOMA-IR, fasting glucose and insulin, triglycerides, LDL- and HDL-cholesterol, OGTT glucose and insulin AUC, SomaScan platform.

REGULATORY AND OPERATIONAL CONSIDERATIONS

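### The primary endpoint, an RCT sample size, is computed from a point estimate of d in about 40 participants, with no interval and no size at a conservative limit

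*Combined protocol and SAP*

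**What the plan says.** The primary endpoint in section 1.33.2 is the sample size required for a later RCT. The effect size behind it is "determined using the observed mean change in BMI from baseline to 16 weeks and the standard deviation for mean change observed" with liraglutide. The plan assumes the same SD in a control group and groups of similar size. On presentation it says: "A plot will be created showing a range of sample sizes required for a between-groups t-test". The worked example takes d = 0.4566 (a difference of 1.58 kg/m² with SD 3.46) and arrives at 120 in total, 60 per group, for one-sided alpha 0.05 and 80% power.

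The hypothesis is "The data will be sufficient to calculate the effect size for change in BMI from baseline to 16 weeks". Two success criteria are stated: "The study will be considered successful if more than 80% complete the trial" (1.33.2) and "Trial success will be based on a p-value <0.05" (1.33.1).

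On intervals, section 1.33.1 says: "Summary statistics will be presented, as well as confidence intervals (Cis), as described in the sections below". Of the later sections, 1.33.2 describes none for the primary endpoint. Section 1.33.3 plans paired t-tests of BMI change without stating an interval. Only 1.33.9 mentions intervals, for exploratory measures that "will be examined using descriptive statistics including confidence intervals when appropriate"; its variable list includes BMI SDS but not BMI change. Section 1.31 caps treated participants at 43 and hopes for 40 completers.

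**The concern.** The pilot exists to produce one number, and the plan would report it without its sampling error. The required size varies with 1/d², so modest error in d becomes large error in the RCT size. A reader given only 120 cannot see that the same data may also be compatible with an RCT several times larger.

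Neither success criterion addresses this. Completion above 80% and p < 0.05 say nothing about how precisely d is known. The hypothesis that the data will be sufficient is nearly empty, because d can be computed from almost any data set. What is at stake is an underpowered RCT, planned on a figure that looks firmer than it is.

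**Working it through.** **Inputs.** Sections 1.31 and 1.33.2 give a liraglutide change of −1.39 kg/m² (SE 0.31, n = 125), a placebo change of +0.19, SD 3.46, 40 completers hoped for and at most 43 treated. The difference is 1.39 + 0.19 = 1.58. The SD follows from 0.31 × √125 = 3.47. Reductions are counted as positive below.

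**The plan's own figure.** d = 1.58/3.46 = 0.4566. The size is the smallest n per group at which a noncentral t with 2n − 2 df and noncentrality d√(n/2) exceeds the one-sided 5% critical value with probability at least 0.80. At n = 60 the power is 0.800 and at n = 59 it is 0.794. So 60 per group, 120 in total, is reproduced.

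**Interval for d at n = 40.** Take the pilot's d as a one-sample standardised change with the control change fixed at +0.19. Then t = 0.4566 × √40 = 2.888 on 39 df. The 95% limits are the values δ for which a noncentral t with noncentrality δ√40 falls at or below 2.888 with probability 0.975 and 0.025. This gives 0.128 to 0.780, a half-width of 0.326. The lower one-sided 80% limit (probability 0.80) is 0.314.

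**RCT totals at those limits (n = 40):**

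| Value of d used | d | RCT total |
|---|---|---|
| Upper 95% limit | 0.780 | 44 |
| Point estimate | 0.4566 | 120 |
| Lower one-sided 80% limit | 0.314 | 254 |
| Lower 95% limit | 0.128 | 1,512 |

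**Consequence of sizing on the point estimate.** Suppose the true d is 0.4566, and let the observed mean and SD both vary over pilots of 40. True RCT power is below 80% when fewer than 60 per group are chosen, and below 70% when fewer than 46 are chosen (power is 0.701 at 46 and 0.693 at 45).

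| Sizing rule | True power below 80% | True power below 70% |
|---|---|---|
| Observed d | 49.8% of pilots | 34.3% |
| Lower one-sided 80% limit of d | 19.4% | 10.6% |

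A simulation of 20,000 pilots gave 49.2% and 33.9% for the first row.

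**Would an upper limit on the SD alone do?** The one-sided 80% factor is √(39/χ²(0.20; 39)) = 1.114. The SD becomes 3.46 × 1.114 = 3.85 and the total 150. About 38% of pilots would still lead to power below 80%, because the error in the mean is left uncorrected.

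**Sensitivity.** The documents give no 16-week effect or SD for this population, so d is varied:

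| n | d | Total at point estimate | Totals across the 95% interval |
|---|---|---|---|
| 40 | 0.4017 (1.39/3.46, control change taken as 0) | 156 | 50 to about 4,180 |
| 40 | 0.6 | 72 | 30 to 370 |
| 40 | 0.8 | 42 | 22 to 130 |
| 43 | 0.4566 | 120 | 44 to 1,268 |
| 35 | 0.4566 | 120 | 40 to 2,242 |

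The n = 35 row is completers only. It is the smallest count that meets the completion criterion with 43 treated (35/43 = 81.4%; 34/43 = 79.1%).

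**Precision of the mean change at n = 40.** The half-width t(0.975; 39) × SD/√40 is 0.80, 1.11 and 1.44 kg/m² for SDs of 2.5, 3.46 and 4.5.

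**The case against.** The strongest reply is that the material is already there. Section 1.33.1 promises N, mean and SD, and a paired t-test is planned on the same BMI change, so anyone can derive an interval. That is true for the mean change, the SD and a one-sample d. But the endpoint is the RCT size, and nothing in the plan carries that uncertainty into it.

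The planned plot might vary d, which would let a reader find the size at a lower value. The example figure cannot be seen in the copy I read. The text does not say what is varied, and a curve of size against power at one fixed d would satisfy it. Even a plot over d would leave the reader to choose the limit.

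A figure of half below 80% power is what any plug-in estimate gives, and both shares assume the RCT adopts the point estimate unchanged, which the plan does not strictly commit to. Both points stand. The one-third below 70% is the more useful warning.

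The example d is borrowed from one year of treatment in adolescents without bariatric surgery. That also stands, so 254 is an illustration and not a target. Changing d alters the range: it is wider at 0.4017, and narrower at 0.6 and 0.8 but still a several-fold spread.

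The most serious reservation is that this trial never observes a control arm, so an interval around the one-sample change could suggest that more uncertainty is covered than really is. This calls for a plain caveat beside the interval. It does not argue for omitting the interval.

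**Conclusion.** The concern holds. The primary deliverable is a point estimate with no planned statement of its precision and no prespecified conservative value. On the plan's own example with 40 completers, a total of 120 stands for a range of 44 to 1,512. An RCT sized on the point estimate would have true power below 70% in about a third of pilots.

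These figures assume d = 0.4566, approximately normal untransformed changes, equal SDs and a control change known to be +0.19. Uncertainty in the control change would widen the range. The arithmetic of the worked example is correct. This should be changed, but it does not affect participants or the conduct of this trial.

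**What to change.** In 1.33.2, report the mean change, SD and d, each with a 95% confidence interval. In the planned plot or a table, show the RCT size at the point estimate and at a prespecified conservative limit of d itself. The lower one-sided 80% limit is one reasonable choice (d about 0.31, total about 254 in the example). What matters is that the limit is fixed in advance. An upper limit on the SD alone is adequate only if the target difference is also fixed in advance.

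In 1.31, state the expected 95% half-widths at n = 40: about 0.33 for d at 0.4566, and about 1.1 kg/m² for the mean change if the SD is 3.46 (0.8 to 1.4 for SDs of 2.5 to 4.5), untransformed.

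Name the scale and the analysis population for d. Section 1.33.1 says "It is expected that log transformation will be used for the primary outcome and most secondary outcomes", while the worked example is in kg/m². The last-observation-carried-forward rule and ITT set in 1.33.3 are specified only for the secondary endpoints. State beside the result that, without a control arm, the interval treats the control mean as known and understates the uncertainty of the between-group effect.

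The cost is SAP wording and a few more output rows, with no change to this trial's size or conduct. The downside is a less favourable planning figure for the RCT, about 254 against 120 in the example.
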